9.6.2.4 Overall Survival

Overall survival (OS) is defined as the number of days from the first dose of rucaparib to the date of death (due to any cause). Patients without a known date of death will be censored on the date the patient was last known to be alive.

The Kaplan-Meier methodology will be used to summarize OS. If able to be estimated, the 50th percentile (median) together with a 95% CI will be presented. The number of patients with events and the number of patients at risk at each timepoint will be presented, and censored patients will be graphically displayed.

9.7 Safety Analyses

All safety analyses will be summarized for the Safety Population.

Safety endpoints are incidence of AEs, clinical laboratory abnormalities, and dose modifications.

AEs, clinical laboratory results, vital signs, ECG results, ECOG performance status, body weight, and concomitant medications/ procedures will be tabulated and summarized.

9.7.1 Extent of Exposure

Duration of exposure will be summarized descriptively and categorically. The number and percentage of patients with dose reductions and dose interruptions will be provided.

9.7.2 Adverse Events

Adverse events will be classified using the Medical Dictionary for Regulatory Activities (MedDRA) classification system. The severity of the toxicities will be graded according to the NCI CTCAE v5.0 or later TEAEs are defined as AEs with onset date on or after the date of first dose of study drug until 28 days after the last dose of study drug.

The number and percentage of patients who experienced TEAEs for each system organ class (SOC) and preferred term will be presented. Multiple instances of the TEAE in each SOC and multiple occurrences of the same preferred term are counted only once per patient. The number and percentage of patients with at least one TEAE will also be summarized.

Separate tables will be presented as follows:

- All TEAEs;
- TEAEs by CTCAE grade;
- Grade 3 or greater TEAEs;
- Treatment-related TEAEs
- Serious TEAEs;
- Treatment-related serious TEAEs;
- TEAEs with an outcome of death;
- TEAEs leading to discontinuation of study;
- TEAEs resulting in interruption/delay of study drug; and TEAEs resulting in dose reduction of study drug.

The incidence of TEAEs will be summarized by relationship to study drug (rucaparib) according to the following categories: “treatment-related,” or “not treatment-related”. If a patient experiences multiple occurrence of the same AE, with different relationship categories for the study drug, the patient will be counted once, as a relationship category of treatment related.

If a patient experiences multiple occurrence of the same AE with different toxicity grades, the patient will be counted once for the maximum (most severe) toxicity grade. AEs with a missing toxicity grade will be presented in the summary table with a toxicity grade of “Missing.” For each toxicity grade, the number and percentage of patients with at least 1 TEAE of the given grade will be summarized.

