3.1.4 Post-treatment Period

Upon treatment discontinuation, regardless of reason (with the exception of withdrawal of consent or death), patients will have an End-of-Treatment (EOT) Visit with assessments as detailed in [Section 7](#).

All patients will be followed for at least 28 days after the last dose of study drug and will then proceed to long-term follow-up (LTFU).

Patients who discontinue treatment for a reason other than disease progression or death should continue to have tumor scans performed at the interval specified until radiological disease progression as assessed by the investigator, death, loss to follow-up, withdrawal from study, study termination, or initiation of subsequent anticancer treatments.

Ongoing serious adverse events (SAEs), AESIs and treatment-related CTCAE Grade 3/4 AEs will be followed until resolution or stabilization has been determined, death, or loss to follow-up. After the 28-Day Follow-Up Visit, only SAEs considered as potentially related to study drug should be reported per Clovis PV requirements and captured in the Clovis Pharmacovigilance (PV) database. This includes serious reports of pneumonitis or similar events, if considered to be related to study drug.

After the 28-day Safety Follow-up Visit, AESIs of MDS and AML, irrespective of causality, should be reported per Clovis PV requirements and captured in the Clovis PV database. AESIs of pneumonitis or similar events should only be reported up to, but not beyond, the 28-day Safety Follow-up Visit.

All patients will be followed for survival and subsequent treatments every 12 weeks (\pm 14 days) relative to the last dose of rucaparib until death, loss to follow-up, withdrawal of consent or study closure.

An optional tumor biopsy will be collected from patients who experience disease progression and provide additional consent.

If a patient begins subsequent anticancer therapy, the sponsor will terminate collection of SAEs, with the exception of the AESIs of MDS and AML.

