- ^m **First dose of study drug in Cycle 1 should be administered within 3 days of enrollment.** Study treatment continues in 28-day cycles until disease progression, unacceptable toxicity, patient or physician request to discontinue, death, initiation of any other cancer therapy, positive pregnancy test, or termination of the study. Study visit should take into account the patient's rucaparib supply. A quantity of rucaparib sufficient to complete 1 cycle (28 days) should be dispensed to the subject/patient on Day 1 of each cycle.
- ⁿ AEs, SAEs, and AESIs that occur after first administration of study drug through to 28 days after last dose of study drug(s). In addition, SAEs that were related to a screening procedure will also be recorded. Ongoing SAEs, AESIs, or treatment-related Grade 3/4 AEs will be followed to resolution or stabilization. After the Safety Follow-up Visit, only SAEs considered as potentially related to study drug (including serious reports of pneumonitis or similar events, ie, interstitial lung disease, pulmonary fibrosis, acute interstitial pneumonitis, alveolitis, hypersensitivity pneumonitis, and organizing pneumonia, if considered to be related to study drug), and the AESIs of MDS and AML regardless of causality, will be recorded in the eCRF. If a patient discontinues from treatment in the rollover study and begins a subsequent anticancer therapy, the sponsor will terminate collection of SAEs.
- ^o Cycles 2 through 6 only. PK samples should be collected prior to the morning dose on the visit days, and as close as possible to 12 hours after the last dose (even if the morning dose on the specified visit days is not administered). If a new treatment cycle is delayed, the predose PK sample closest to 12 hours after the last dose should still be collected on that visit and should not be collected on Day 1 of the delayed treatment cycle. Refer to the Laboratory Manual for detailed sample collection and handling instructions.

- p An optional tumor biopsy may be collected from patients within 30 days after the time of disease progression or treatment discontinuation. Additional consent is required. Refer to the Laboratory Manual for detailed sample collection and handling instructions.

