- q All patients discontinued from treatment, regardless of reason, should be followed for subsequent treatments, secondary malignancy, and survival every 12 weeks relative to the last dose of study drug until death, loss to follow-up, withdrawal of consent from study, or closure of the study. Follow-up can be performed via the telephone and can be completed to coincide with scheduled tumor assessments during this period. Diagnosis of any secondary malignancy requires appropriate documentation (ie, laboratory and/or pathology reports).

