After the 28-day Safety Follow-up Visit, AESIs of MDS and AML, irrespective of causality, should be reported per Clovis PV requirements and captured in the Clovis PV database. AESIs of pneumonitis or similar events should only be reported up to, but not beyond, the 28-day Safety Follow-up Visit.

Information on the follow-up of AEs, SAEs, and AESIs is provided in [Section 8.8](#).

In order to avoid vague, ambiguous, or colloquial expressions, the AE should be recorded in standard medical terminology rather than the patient's own words. Whenever possible, the investigator should combine signs and symptoms that constitute a single disease entity or syndrome into a final diagnosis, if appropriate. For example, fever, cough, and shortness of breath may be reported as pneumonia, if that is a reasonable diagnosis.

Each AE is to be evaluated for **causal relationship** to the investigational drug, severity, and seriousness. The action taken and the outcome must also be recorded.

SAEs and AESIs that occur during the study or within 28 days after receiving the last dose of rucaparib, whether or not related to rucaparib, must be reported immediately (ie, **within 24 hours** of knowledge of the event or additional information for a previously-reported event) to the sponsor/SAE designee. The contact information for reporting of SAEs/AESIs can be found on the SAE/AESI Reporting Form.

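### Late MDS/AML is collected through long-term follow-up, but every adverse-event summary specified in protocol Section 9.7.2 stops at 28 days after the last dose

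*Combined protocol and SAP*

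**What the plan says.** **Collection.** Section 1.1.7.1 makes MDS and AML events of special interest. Section 3.1.4 states: "After the 28-day Safety Follow-up Visit, AESIs of MDS and AML, irrespective of causality, should be reported per Clovis PV requirements". Section 8.7 repeats the requirement and names the pharmacovigilance database as the place of capture. Footnote n to Table 5 (Section 7.1) says that, after the Safety Follow-up Visit, "the AESIs of MDS and AML regardless of causality, will be recorded in the eCRF". The synopsis lists MDS, AML, treatment-related SAEs and secondary malignancy among the items followed every 12 weeks. Section 3.1.4 ends SAE collection once a new anticancer therapy begins, but excepts MDS and AML.

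**Analysis.** Section 9.7.2 gives this definition of TEAEs: "AEs with onset date on or after the date of first dose of study drug until 28 days after the last dose of study drug". Its main table follows from that: "The number and percentage of patients who experienced TEAEs for each system organ class (SOC) and preferred term will be presented". The list of separate tables closes with "TEAEs resulting in interruption/delay of study drug; and TEAEs resulting in dose reduction of study drug", and every item before these is also a TEAE table.

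**The concern.** The analysis window is shorter than the collection window for the one class of event that the protocol singles out for long-term tracking. Table 1 justifies the safety objective by evaluation of both acute and long-term risk, and Section 1.2.2 says the study is meant to support a tumor-agnostic indication. If the tables are produced exactly as Section 9.7.2 lists them, a patient who develops MDS or AML three months after stopping rucaparib is reported to the sponsor but counted in none of them. Someone who reads the adverse-event tables for the risk of MDS/AML would see only cases from the treatment period plus 28 days.

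**Working it through.** There is no stated figure to reproduce. The check is a comparison of scope, followed by an illustration of scale.

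**Step 1. What is collected after day 28.**
- MDS/AML, irrespective of causality: synopsis, Sections 3.1.4, 7.3.4.1, 8.7 and 8.8, and Table 5 footnote n.
- SAEs potentially related to rucaparib: the same places.
- Secondary malignancy: synopsis and Table 5 footnote q.
- Follow-up ends at death, loss to follow-up, withdrawal of consent or study closure.

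**Step 2. What is summarized.**

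| Summary in Section 9.7.2 | Events included |
|---|---|
| System organ class and preferred term | TEAEs |
| Patients with at least one event | TEAEs |
| Ten listed tables: all; by grade; Grade 3 or greater; related; serious; related serious; fatal; leading to discontinuation; to interruption or delay; to dose reduction | TEAEs |
| By relationship to rucaparib | TEAEs |
| By maximum grade | TEAEs |

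No row reaches an event with onset more than 28 days after the last dose. Sections 9.7, 9.7.1, 9.7.3 to 9.7.5 and 9.9 add no table or listing of events of special interest, secondary malignancies or later adverse events. By contrast, Sections 9.7.3 and 9.7.4 expressly send later laboratory values and vital signs to listings. Adverse events have no such rule.

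**Step 3. The data route.** Sections 3.1.4 and 8.7 name the pharmacovigilance database for late MDS/AML. Sections 7.3.4.1 and 8.7 describe entry on the AE eCRF only through 28 days after the last dose. Footnote n requires eCRF entry of late MDS/AML. These can all be followed together, but only footnote n puts the late cases in the clinical database.

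**Step 4. Scale, under assumed rates.** The documents give no rate of MDS/AML and no latency. Let p be the assumed proportion of treated patients with onset after the window. Expected cases are N × p, and the chance of at least one is 1 − (1 − p)^N. N is 220 (approximate maximum enrollment) or 30 (minimum), from Section 9.2.

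| p (assumed) | N = 220: expected | N = 220: chance of ≥ 1 | N = 30: expected | N = 30: chance of ≥ 1 |
|---|---|---|---|---|
| 0.5% | 220 × 0.005 = 1.1 | 1 − 0.995^220 = 67% | 30 × 0.005 = 0.15 | 1 − 0.995^30 = 14% |
| 1% | 220 × 0.01 = 2.2 | 1 − 0.99^220 = 89% | 30 × 0.01 = 0.3 | 1 − 0.99^30 = 26% |
| 2% | 220 × 0.02 = 4.4 | 1 − 0.98^220 = 99% | 30 × 0.02 = 0.6 | 1 − 0.98^30 = 45% |

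Each such case would contribute zero to the Section 9.7.2 tables.

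**The case against.** **The SAP may supply the table.** Section 9.1 defers further detail to a separate SAP, whose text is not in the documents. A table or listing of events of special interest is the kind of thing a SAP adds. This stands as a limit: a reader might infer that late MDS/AML is missing from every planned output, and the documents cannot show that. What can be said is that the protocol specifies its adverse-event tables one by one and none reaches these events.

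**Section 9.7 already promises that AEs will be tabulated and summarized.** It does, in general terms, and gives incidence of AEs as an endpoint. Section 9.7.2 then carries this out with TEAEs only, so the general sentence does not close the gap.

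**The database instructions do not conflict.** A reader might infer that sites following Sections 3.1.4 and 8.7 would keep late cases out of the eCRF. Neither section says the pharmacovigilance database is the only destination, and Table 5 marks events of special interest for collection in long-term follow-up. This objection stands: the wording needs aligning, but no loss of data is shown.

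**Footnote q does not drop MDS/AML.** It says that patients "should be followed for subsequent treatments, secondary malignancy, and survival every 12 weeks relative to the last dose of study drug" and does not name MDS or AML. The Table 5 row listing long-term follow-up items does name events of special interest, and so the omission is minor wording.

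**A table labeled treatment-emergent is not wrong on its own terms.** This is correct. Understatement would arise only if its count were presented as the total incidence, and nothing in the text says it would be. Section 1.1.7.1 also regards a causal link to rucaparib as unproven. Since late collection is irrespective of causality, that is no reason to leave the cases out of the summary.

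**Conclusion.** The point holds as a gap in the protocol's analysis section. Late MDS/AML is collected on purpose, yet no adverse-event table or listing specified in the protocol would show it. Cases with onset inside the window would appear under system organ class and preferred term, though not as a separate summary. Late treatment-related SAEs and secondary malignancies share the gap.

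The size is not known. The illustrative 1.1 to 4.4 cases in 220 patients (0.15 to 0.6 in 30) rest wholly on assumed late rates of 0.5% to 2%. It is also tempting to state what share of all MDS/AML cases the tables would miss. That would need mean time on drug, mean follow-up and the shape of the hazard over time. The documents give none of these; the median progression-free survival of 9.1 months in Section 1.1.6 comes from maintenance treatment in pancreatic cancer and is not a mean time on drug in this mixed population.

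The gap in scope does not depend on any of these assumptions. It does depend on the SAP not already containing such a table.

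**What to change.** In Section 9.7.2, and in the SAP, add one table and a listing in the Safety Population of MDS/AML with onset at any time from first dose to end of follow-up. Show:
- the number and percentage of patients;
- time from first dose to onset;
- whether onset was within or after 28 days of the last dose;
- as a separate measure, the rate per total follow-up time.

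List late treatment-related SAEs and secondary malignancies in the same way.

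State in Sections 3.1.4, 7.3.4.1 and 8.7 that MDS/AML after day 28 is entered in the eCRF as well as the pharmacovigilance database, to match Table 5 footnote n.

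The cost is one extra table with its listing and a few sentences of wording. The events are already collected, and sample size and error rates are unaffected. The drawback for the sponsor is that the reported incidence of MDS/AML may be less favorable.

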6. To evaluate the safety and tolerability of rucaparib.	6. Incidence of adverse events, clinical laboratory abnormalities and dose modifications.	6. In accordance with International Council for Harmonisation (ICH) E9 principles, acute and long-term evaluation of medical risks including adverse events (AEs), laboratory tests, vital signs and other special safety tests (eg, ECGs) will be assessed.
7. To evaluate steady-state PK of rucaparib.	7. Steady-state minimum concentration (C_{min}).	7. Sparse PK allows for monitoring of rucaparib exposure in various cancer types and exploratory exposure response analysis.

Table 1. Study Objectives and Endpoints

Objectives	Endpoints	Justifications

Exploratory Objectives
 
1. To assess resistance mutations detected in circulating tumor DNA (ctDNA).
 
2. To evaluate zygosity of deleterious mutations detected in HRR genes within tumor tissue.
	
Exploratory Endpoints
 
1. Best overall response, DOR and PFS summarized in patients with and without resistance mutations in ctDNA.
 
2. Best overall response, DOR and PFS summarized in patients with homozygous vs heterozygous mutations in HRR genes.
	
Justification for Exploratory Endpoints
 
1. Primary and acquired resistance mutations to rucaparib have been identified in ctDNA from ovarian and prostate cancer patients. This objective will evaluate if these resistance mutations have an impact on rucaparib clinical efficacy across tumor types.
 
2. HRD typically results from biallelic inactivation of an HRR gene. This exploratory objective will evaluate if patients with homozygous mutations in HRR genes derive greater rucaparib clinical efficacy.

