3.3 Removal of Patients from Therapy or Assessment

A patient must be discontinued from protocol-prescribed therapy if any of the following apply:

- Consent withdrawal for any reason at the patient's own request, or at the request of their legally authorized representative (where acceptable according to national law and/or local regulations);
- Progression of patient's underlying cancer per RECIST v1.1, or modified RECIST v1.1/PCWG3 guidelines for prostate cancer, as assessed by the investigator, unless the patient continues to derive clinical benefit from the study drug(s) according to the investigator, the investigator has consulted with the sponsor's medical officer or designee, and the patient has provided additional consent for treatment beyond progression at the next study visit;
- Any event, adverse or otherwise, that, in the opinion of the investigator, would pose an unacceptable safety risk to the patient;
- An intercurrent illness that, in the opinion of the investigator, would affect assessments of the clinical status to a significant degree and requires discontinuation of therapy;
- Noncompliance by the patient with protocol-mandated procedures;
- Study termination; or
- A positive pregnancy test at any time during the study.

Discontinuation of treatment does not necessarily indicate study discontinuation for a patient. Samples collected for research will continue to be used unless the patient explicitly withdraws consent for their use. Information that is collected while the patient has consented to be in the study cannot be withdrawn. Details are provided in the Informed Consent Form (ICF).

[figure not shown]
If the patient withdraws consent to continue in the study or discontinues the study for another reason it will be documented on the appropriate eCRF. A patient may withdraw consent to participate in an additional or optional part of a study that has a corresponding consent (ie, optional tumor biopsy) yet continue to participate and be treated/followed in the main part of the study.

The sponsor may discontinue the study early for any of the reasons noted in [Section 10.6](#).

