5.6.4 Rucaparib Discontinuation

Rucaparib should be permanently discontinued for any of the following:

- If a patient continues to experience toxicity despite dose reduction steps to the lowest permissible dose or if dosing is interrupted for > 21 consecutive days due to toxicity, treatment with rucaparib should be discontinued, with the following exceptions:
 - Treatment interruption > 21 days may be allowed if approved by the sponsor. Prior to re-initiating treatment for a patient with a treatment interruption lasting > 21 days, the study medical monitor/designee must be consulted. Tumor assessments should continue as per protocol even if treatment is interrupted.
- Confirmed diagnosis of MDS or AML;
- Any AE, laboratory abnormality, or intercurrent illness which, in the judgment of the investigator, presents a substantial clinical risk to the patient with continued oral study treatment dosing; or
- Patient with progressive disease. If a patient receiving study drug has met criteria for radiologic disease progression by RECIST v1.1 criteria (or modified RECIST v1.1 criteria for mCRPC patients), but continues to derive clinical benefit per the investigator, continuation of treatment may be permitted after discussion with the sponsor.

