8.7.5 Outcome and Action Taken

The investigator will record the action taken and outcome for each AE according to the following criteria:

Action Taken with Study Drug (note all that apply)

- Drug withdrawn;
- Dose reduced;
- Dose interrupted;
- Dose not changed;
- Unknown; or
- Not applicable.

Outcome

- Recovered/resolved;
- Recovering/resolving;

- Not recovered/Not resolved;
- Recovered/resolved with sequelae;
- Fatal; or
- Unknown/ Lost to follow-up.

8.8 Follow-up of Adverse Events, Serious Adverse Events, and Adverse Events of Special Interest

All AEs (including SAEs and AESIs) occurring during the study are to be followed up in accordance with good medical practice until resolved; judged no longer clinically significant; or, if a chronic condition becomes the patient's new baseline, until fully characterized through 28 days after the last dose of rucaparib. Any SAEs, AESIs, and treatment-related Grade 3/4 AEs must be followed until resolution or stabilization, death, or until loss to follow-up. After the 28-day safety follow-up window, SAEs considered as potentially related to rucaparib (including serious reports of pneumonitis or similar events, ie, interstitial lung disease, pulmonary fibrosis, acute interstitial pneumonitis, alveolitis necrotizing, alveolitis, hypersensitivity pneumonitis, and organizing pneumonia, if considered to be related to study drug), and the AESIs of MDS and AML irrespective of causality, must be reported.

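### Section 9.7.2 lists a table of TEAEs leading to discontinuation of the study, probably meaning study drug; as written, no listed table shows by term which TEAEs ended rucaparib treatment

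*Combined protocol and SAP*

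**What the plan says.** Section 9.7.2 lists the separate TEAE tables to be produced. The discontinuation item reads "TEAEs leading to discontinuation of study". The items that follow it are "TEAEs resulting in interruption/delay of study drug; and TEAEs resulting in dose reduction of study drug". The list has no item for TEAEs that led to stopping rucaparib.

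Elsewhere the protocol keeps the two kinds of discontinuation apart. Section 3.3 states: "Discontinuation of treatment does not necessarily indicate study discontinuation for a patient". Section 3.1.4 states: "All patients will be followed for at least 28 days after the last dose of study drug and will then proceed to long-term follow-up". A footnote to the Schedule of Assessments in Section 7.1 adds: "All patients discontinued from treatment, regardless of reason, should be followed for subsequent treatments, secondary malignancy, and survival every 12 weeks".

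For each adverse event, Section 8.7.5 has the investigator record the action taken with study drug. One of the options is "Drug withdrawn".

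**The concern.** Toxicity is an expected route off treatment. Section 5.6.4, for example, says that "if dosing is interrupted for > 21 consecutive days due to toxicity, treatment with rucaparib should be discontinued", subject to a sponsor-approved exception. Such a patient normally moves to the safety follow-up visit and then to long-term follow-up, and so has stopped the drug without leaving the study. A table defined by study discontinuation does not count that patient.

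Safety and tolerability is a secondary objective. A reader of the study report will expect to see which events made patients stop rucaparib, and how often. If the listed wording is programmed literally, that breakdown is not produced, and the table in its place answers a different question under a similar title.

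**Working it through.** No arithmetic applies: the documents attach no figure to this item. The check is to set the relevant sections side by side.

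1. **What the item counts.** Section 9.7.2 names the study for discontinuation, but study drug for interruption and for dose reduction. Within one list, the wording changes for one item only.

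2. **Whether the two events coincide.** They do not. Section 3.3 says so directly. Section 3.1.4 sends patients to at least 28 days of follow-up after the last dose and then to long-term follow-up. The Section 7.1 footnote continues contact every 12 weeks whatever the reason for stopping treatment, until death, loss to follow-up, withdrawal of consent or study closure.

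3. **Who is in the literal table.** It would hold patients whose TEAE ended their participation in the study. Fatal TEAEs do that, but they have their own table in the same list. A patient who stops rucaparib for a TEAE and continues in follow-up is left out.

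4. **Whether another listed summary fills the gap.**
   - Section 9.7.1 (exposure) reports patients with dose reductions and interruptions, not permanent discontinuations.
   - The safety endpoint in Section 2, Table 1, is "Incidence of adverse events, clinical laboratory abnormalities and dose modifications". Section 5.6.1 explains dose modification as interruption, reduction or re-escalation, so permanent discontinuation is outside it.
   - Section 9.4 (disposition) gives the number discontinued and the primary reason. It does not say whether this means treatment or study, and it is not broken down by adverse event term.
   - The interruption table in Section 9.7.2 would catch some of these TEAEs if dosing was held first, but would not identify them as the reason for stopping.
   - The tables of all TEAEs, by grade and by relationship include these events without marking them as the cause of discontinuation.

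5. **Whether the data exist.** Section 8.7.5 records drug withdrawal for each adverse event, so a table of TEAEs that ended rucaparib treatment can be built directly. The same list has no category for an event that led to leaving the study, and the protocol describes no other link between an adverse event and study exit. The table as worded is therefore harder to derive than the one that is missing.

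**Result.** On the wording of Section 9.7.2, the incidence by system organ class and preferred term of TEAEs leading to rucaparib discontinuation is not among the listed outputs, although the data for it are collected.

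**The case against.** The strongest reply is that this is a dropped word and not a choice of analysis. The neighbouring items say study drug. Section 10.5 also speaks loosely of a patient withdrawn from the study because of a treatment-limiting adverse event, where stopping treatment is the natural meaning. The per-event field available to a programmer is drug withdrawal, so the table actually produced may well be the right one. This stands as an account of how the wording arose and of why harm is uncertain. It does not make the text correct: Section 3.3 separates the two events, so the analysis section should too.

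The second reply is that little is lost. The TEAEs remain in the other tables, disposition may count some of the patients, and Section 9.1 defers further detail to a separate SAP whose text is not part of the combined document. This also stands, and it limits the point to one missing breakdown in the protocol's own list.

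A reader might go further and infer that the main tolerability table will be almost empty, or that discontinuation for toxicity will be understated by some stated percentage. The documents support neither. They do not rank the safety tables, and the safety endpoints do not name discontinuation for adverse events. They give no rate of stopping rucaparib for an adverse event from which a shortfall could be computed, and an almost empty table presupposes literal programming, which the action-taken field makes less likely.

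**Conclusion.** Wrong as written, and minor. The item names study discontinuation where the rest of the list and the data collection point to discontinuation of study drug. Followed literally, it omits patients who stop rucaparib for a TEAE and remain in follow-up, and no other listed summary reports those TEAEs by term.

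No numerical size is attached. The conclusion rests on two conditions: that the item is read as it stands, and that the separate SAP does not already correct it. It does not imply that safety data are lost or that the secondary safety objective goes unmeasured. Safety summaries in this single-arm study are descriptive, and nothing here touches efficacy, eligibility or patient care.

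**What to change.** - In Section 9.7.2, add the word *drug* to the end of the discontinuation item, and state that the table is derived from the action-taken category "Drug withdrawn" in Section 8.7.5.
- If the sponsor also wants TEAEs associated with leaving the study, list that as a separate item and say how an event is linked to study exit.
- In Section 9.4, state whether the disposition summary reports discontinuation of treatment, discontinuation of the study, or both.
- Check the separate SAP and its table shells for the same wording and align them.

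The cost is a one-word correction and a clarifying sentence or two. No new data are needed, and the change can be made in the SAP or table shells if the protocol is not otherwise being amended.
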